1.3 Rationale

Although sunitinib has anti-angiogenic properties and has activity against several kinases, Sunitinib has been approved for patients with metastatic GIST who are resistant to imatinib. Few studies have evaluated sunitinib in melanomas with cKIT mutations, but response has been observed, and otherwise this agent has not been evaluated in other malignancies with cKIT mutations. The numbers of patients with a cKIT mutation in each type of malignancy is relatively small, making it difficult to establish response among specific types of malignancies.

The MATCH trial aims to establish whether patients whose tumors harbor mutations in specific pathways of interest benefit (as defined as objective response) from agents targeting that pathway, irrespective of tumor type. This trial will allow detection of a sufficient cohort of patients to determine the effect of sunitinib on tumors with cKIT mutations, and allow investigation of whether agents likely to have activity against a molecular alteration in one disease will exhibit similar activity in other diseases with the same molecular alterations.

1.4 Objectives

Primary:

- a) Observe response rate in patients with c-KIT mutations treated with sunitinib Secondary:
- a) Observe 6-month progression free survival of patients with c-KIT mutations treated with sunitinib
- b) Observe time to progression of patients with c-KIT mutations treated with sunitinib
- c) Document toxicities in patients with c-KIT mutations treated with sunitinib

2. Selection of Patients

FCOG-ACRIN Patient No.

Each of the criteria in the checklist that follows must be met, along with the eligibility in the MATCH Master Protocol, in order for a patient to be considered eligible for this study. Use the checklist to confirm a patient's eligibility. For each patient, this checklist must be photocopied, completed and maintained in the patient's chart.

In calculating days of tests and measurements, the day a test or measurement is done is considered Day 0. Therefore, if a test is done on a Monday, the Monday four weeks later would be considered Day 28.

	Patient's	Initials (L, F, M)	
	Physiciar	n Signatı	ure and Date	
crit Th exc Se stu qu Gro		criteria There excep Section study, questing Group	licy does not allow for the issuance of waivers to any protocol specified teria (http://ctep.cancer.gov/protocolDevelopment/policies deviations.htm). erefore, all eligibility criteria listed in Section 2 must be met, without ception. The registration of individuals who do not meet all criteria listed in ction 2 can result in the participant being censored from the analysis of the idy, and the citation of a major protocol violation during an audit. All estions regarding clarification of eligibility criteria must be directed to the oup's Executive Officer ([contact]) or the oup's Regulatory Officer ([contact]).	
	NOTE:	been ı	tions may use the eligibility checklist as source documentation if it has reviewed, signed, and dated prior to registration/randomization by the ng physician.	
	NOTE:	All pat	tients must have signed the relevant treatment consent form	
	2.1 E	ligibility	Criteria	
Rev.2/16	2.	1.1	Patients must fulfill all eligibility criteria outlined in Section 3.1 of MATCH Master Protocol (excluding Section 3.1.6) at the time of registration to treatment step (Step 1, 3, 5, 7).	
Rev. Add13 Rev. Add25	2.	1.2	Patients must have a somatic cKIT mutation in exon 9, 11, 13 or 14, excluding exon 17 or 18 mutations, activating PDGFRA or PDGFRB variants and fusions, or another aberration, as identified via the MATCH Master Protocol and described in Appendix II. See Appendix II	
			Actionable Mutations of Interest (aMOIs)for information on the inclusion and exclusion mutations, along with the corresponding Levels of Evidence (LOE).	
	2.	1.3	Patient must have normal organ and marrow function as defined below: Total bilirubin must be within normal institutional limits. Creatinine must be within normal institutional limits. OR	

		Creatinine clearance \geq 60 mL/min/1.73 m ² for patients with creatinine levels above institutional normal.
		Creatinine Clearance:
		 Serum Calcium must be ≤ 12.0 mg/dL.
	2.1.4	Patients must have an electrocardiogram (ECG) within 8 weeks prior to treatment assignment and must have no clinically important abnormalities in rhythm, conduction or morphology of resting ECG (e.g. complete left bundle branch block, third degree heart block):
		Date of ECG:
Rev. 2/16	2.1.5	Patients with known left ventricular dysfunction must have ECHO or a nuclear study (MUGA or First Pass) within 4 weeks prior to registration to treatment and must not have left ventricular ejection fraction (LVEF) < institutional lower limit of normal (LLN). If the LLN is not defined at a site, the LVEF must be > 50% for the patient to be eligible.
		2.1.5.1 The following groups of patients are eligible provided they have New York Heart Association Class II cardiac function on baseline ECHO/nuclear study:
		 Patients with a history of Class II heart failure who are asymptomatic on treatment
		 Patients with prior anthracycline exposure
		 Patients who have received central thoracic radiation that included the heart in the radiotherapy port
		Date of ECHO/nuclear study:
		NOTE: Pre-treatment LVEF determination in patients without known left ventricular dysfunction (or per Section 2.1.5.1) is NOT otherwise required.
	2.1.6	Patients with any of the following conditions are excluded:
		 Serious or non-healing wound, ulcer, or bone fracture
		 History of abdominal fistula, gastrointestinal perforation, or intra- abdominal abscess within 28 days of treatment
		 Any history of cerebrovascular accident (CVA) or transient ischemic attack within 12 months prior to study entry
		 History of myocardial infarction, cardiac arrhythmia, stable/unstable angina, symptomatic congestive heart failure, or coronary/peripheral artery bypass graft or stenting within 12 months prior to study entry
		 History of pulmonary embolism within the past 12 months
	2.1.7	Patients must not have known hypersensitivity or excess toxicity from sunitinib or compounds of similar chemical composition or biologic effect. This list includes, but is not limited to, patients with significant cardiac or hepatic toxicity from multikinase inhibitors with similar kinase inhibitory profiles (sorafenib, regorafenib, pazopanib).

	NCI Update Date: August 12, 2015
	Questions regarding a significant intolerance to a prior therapy should be directed to the sub-protocol PI.
2.1.8	Patients must not have had prior therapy with sunitinib.
2.1.9	Patients must not have planned ongoing administration of STRONG and MODERATE CYP3A4 inhibitors or inducers. See Appendix V (and Appendix VI of the MATCH Master Protocol). The reference list of cytochrome p450 (CYP) isozymes and classification of strong, moderate, and weak interactions is available through the FDA website:
	http://www.fda.gov/Drugs/DevelopmentApprovalProcess/Development
	Resources/DrugInteractionsLabeling/ucm093664.htm
	 Strong CYP3A4 inhibitors are not permitted within 7 days before dosing and should be avoided throughout the study.
	 Strong CYP3A4 inducers are not permitted within 12 days before dosing and should be avoided throughout the study.
2.1.10	Patients must not have GIST, renal cell carcinoma, or pancreatic neuroendocrine tumor
2.1.11	Patients must not have a NCI CTCAE version 4 grade 3 hemorrhage within 4 weeks of starting study treatment
2.1.12	Patients must not have hypertension that cannot be controlled by medications (> 140/90 mmHg despite optimal medical therapy)
2.1.13	Patients must not have pre-existing thyroid abnormality with thyroid function that cannot be maintained in the normal range with medication
2.1.14	Participants may not have a major surgical procedure, open biopsy, or significant traumatic injury within 28 days prior to starting sunitinib.
2.1.15	Patients with known brain metastases should be excluded from this clinical trial because of their poor prognosis and because they often develop progressive neurologic dysfunction that would confound the evaluation of neurologic and other adverse events.
2.1.16	Patients who require therapeutic doses of coumarin derivative anticoagulants such as warfarin are excluded, although doses up to 2 mg daily are permitted for prophylaxis of thrombosis.
	NOTE : Low molecular weight heparin is permitted provided that the patient's PT INR is < 1.5.

EAY131-V

Version Date: November 10, 2022

OPTIONAL:

This signature line is provided for use by institutions wishing to use the eligibility checklist as source documentation.

Date

Physician Signature

3. Sunitinib Treatment Plan

3.1 Administration Schedule

Sunitinib is dosed at 50mg po, daily, regardless of ideal or actual body weight.

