Recent studies have shown that sunitinib may have activity in patients with other tumors that have c-KIT mutations, such as melanoma. There are three phase II studies demonstrating response to imatinib for melanomas harboring KIT mutations of approximately 20-29% [Carvajal et al., 2011, Guo et al., 2011, Hodi et al., 2013]. In a phase II study of sunitinib in melanoma patients, of the four evaluable patients with KIT mutations, 1 had a complete remission for 15 months and 2 had partial responses (1- and 7-month duration) [Minor et al., 2012]. The tolerability and toxicity of sunitinib was similar to that reported in renal cell cancer and GISTs.

Efficacy according to genotype

It is known that GIST responsiveness to imatinib varies by primary KIT genotype; exon 11-mutant GISTs are more sensitive to imatinib than exon 9-mutant GISTs. Heinrich et al. (2008) conducted a study which evaluated the clinical activity of sunitinib based on GIST kinase genotype. When evaluating primary tumor genotype, the objective response to sunitinib was more common in patients with KIT exon 9 than exon 11 mutant GISTs (37% vs 5%, p=0.002), and the median progression-free survival (PFS) was significantly longer for patients with exon 9 mutations compared to those with exon 11 mutations (19.4 months vs 5.1 months, p=0.0005). Median overall survival was also significantly longer for patients with exon 9 mutations (26.9 months vs 12.3 months, p=0.012). Among those with secondary tumor genotype, clusters of mutations occurred in exons 13 and 14, as well as exon 17. The median PFS with sunitinib was significantly longer for those with secondary KIT exon 13 or 14 mutations, than for those with exon 17 or 18 mutations (7.8 months vs 2.3 months, p=0.016). Furthermore, Gajiwala et al. (2009) demonstrated biochemically that GISTs with exon 17 mutations are strongly resistant to sunitinib. These mutants bind sunitinib in the inactivated form but are then converted to the active drug-resistant form. We will exclude patients with exon 17 and 18 cKIT mutations from this trial.

KIT inhibitors in other malignancies

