Appendix II

Actionable Mutations of Interest (aMOIs)

List of Inclusion Variants:

A function has been implemented in MATCHBOX to identify any in-frame insertions and deletions in exon 9, 11, 13, and 14 of the KIT gene at Level of Evidence code 2. This function may include any in-frame insertions, deletions or known activating missense mutations in exons 9, 11, 13, and 14 of the KIT gene at Level of Evidence code 2. Please refer to Section 1.4.2 of the MATCH Master Protocol for more information.

Gene Name	Variant ID	Variant Type	Level of Evidence Code	аМОІ
KIT	COSM1326	Large Indel	2	p.S501_A502insAY
KIT	COSM27901	Large Indel	2	p.P551_V560delinsL
KIT	COSM1198	Large Indel	2	p.V555_V559del
KIT	COSM1230	Large Indel	2	p.W557_V560delinsF
KIT	COSM1234	Large Indel	2	p.K558_V560del
KIT	COSM1238	Large Indel	2	p.K558_N564del
KIT	COSM1235	Large Indel	2	p.K558_V559del
KIT	COSM1248	Large Indel	2	p.V559_V560del
KIT	COSM1262	Indel	2	p.E561del
KIT	COSM23560	Large Indel	2	p.N564_Y578del
KIT	COSM1281	Large Indel	2	p.V569_Q575del
KIT	COSM144983	Large Indel	2	p.T500_S501insSA
KIT	COSM219786	Large Indel	2	p.T500_S501insSA
KIT	COSM53306	Large Indel	2	p.S501_A502insAF
KIT	COSM1164	Large Indel	2	p.K550_V555delinsI
KIT	COSM1172	Large Indel	2	p.P551_E554del
KIT	COSM1169	Large Indel	2	p.Pro551_Val555del
KIT	COSM1170	Large Indel	2	p.P551_Q556del
KIT	COSM1171	Indel	2	p.P551del
KIT	COSM1174	Large Indel	2	p.P551_V555delinsL
KIT	COSM1176	Indel	2	p.P551_M552delinsL
KIT	COSM36304	Large Indel	2	p.M552_D572del
KIT	COSM1177	Large Indel	2	p.M552_W557del
KIT	COSM96881	Large Indel	2	p.M552_Y553del
KIT	COSM1182	Large Indel	2	p.M552_K558del
KIT	COSM1180	Large Indel	2	p.M552_W557del
KIT	COSM18827	Large Indel	2	p.M552_V555del
KIT	COSM1179	Large Indel	2	p.M552_Y553del
KIT	COSM1181	Large Indel	2	p.M552_E554del

Gene Name	Variant ID	Variant Type	Level of Evidence Code	аМОІ
KIT	COSM1327	Large Indel	2	p.M552_Q556del
KIT	COSM96880	Large Indel	2	p.M552_E561delinsK
KIT	COSM36311	Large Indel	2	p.M552_E554delinsK
KIT	COSM96868	Large Indel	2	p.M552_Q556delinsK
KIT	COSM96863	Indel	2	p.M552_Y553delinsN
KIT	COSM133636	Large Indel	2	p.M552_W557delinsR
KIT	COSM1185	Large Indel	2	p.M552_V555delinsI
KIT	COSM1190	Large Indel	2	p.M552_W557del
KIT	COSM1187	Large Indel	2	p.M552_W557delinsK
KIT	COSM1189	Large Indel	2	p.M552_Q556delinsK
KIT	COSM1191	Large Indel	2	p.Y553_V559del
KIT	COSM22275	Large Indel	2	p.Y553_T574delinsS
KIT	COSM96947	Large Indel	2	p.E554_N564del
KIT	COSM36294	Large Indel	2	p.E554_D572del

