KIT	COSM133700	SNV	3	p.W557C
KIT	COSM19108	SNV	3	p.W557C
KIT	COSM30551	SNV	3	p.K558E
KIT	COSM1246	SNV	3	p.K558N
KIT	COSM1255	SNV	3	p.V559A
KIT	COSM1253	SNV	3	p.V559G
KIT	COSM36302	SNV	3	p.V560A
KIT	COSM1264	SNV	3	p.E561K
KIT	COSM133701	SNV	3	p.R586K
KIT	COSM5702513	SNV	3	p.S628N
KIT	COSM1600403	SNV	3	p.R634W
KIT	COSM96871	SNV	3	p.K642Q
KIT	COSM133675	SNV	3	p.G663E
KIT	COSM36053	SNV	3	p.H697Y
KIT	MVAR183	SNV	3	p.H802T
KIT	COSM18681	SNV	3	p.Y823D
KIT	COSM24637	SNV	3	p.F469L
KIT	COSM24639	SNV	3	p.N486D
KIT	COSM24638	SNV	3	p.V489A
KIT	COSM29015	SNV	3	p.K558R
KIT	COSM1246	SNV	3	p.K558N
PDGFRA	MVAR189	Indel	3	p.W559_R560del
PDGFRA	COSM739	SNV	3	p.V561D
PDGFRA	COSM742	Indel	3	p.S566_E571>R
PDGFRA	COSM12418	Indel	3	p.S566_E571>R
PDGFRA	COSM30546	Indel	3	p.S566_E571>R
PDGFRA	COSM22414	SNV	3	p.N659K
PDGFRA	COSM22415	SNV	3	p.N659K
PDGFRA	COSM743	SNV	3	P.T674I
PDGFRA	COSM12397	SNV	3	p.D842Y
PDGFRA	COSM737	Indel	3	p.I843_D846delIMHD
PDGFRA	COSM12396	SNV	3	p.D842Y
PDGFRA	COSM96892	Indel	3	p.I843_D846delIMHD
PDGFRA	COSM12400	Indel	3	p.I843_D846delIMHD

Gene Name	Variant ID	Variant Type	Level of Evidence Code	аМОІ
PDGFRA	COSM12407	Indel	3	p.l843_S847>T
PDGFRA	COSM4969655	Indel	3	p.l843dell
PDGFRA	COSM738	Indel	3	p.H845_N848>P
PDGFRA	COSM12399	SNV	3	p.D846Y
PDGFRA	COSM94952	SNV	3	p.Y849C
PDGFRB	VCV00037555 7	InDel	3	p.I538_L539insR
PDGFRB	VCV00005584 8	SNV	3	p.R561C
PDGFRB	VCV00037568 2	SNV	3	p.W566R
PDGFRB	VCV00037555 5	Indel	3	p.W566_V568delinsL
PDGFRB	COSM6916840	SNV	3	p.N666K
PDGFRB	COSM6927334	SNV	3	p.D850V
PDGFRA	BCR- PDGFRA.B12i ns12P12	Fusion	3	BCR-PDGFRA.B12ins12P12
PDGFRA	BCR- PDGFRA.B1P1 3	Fusion	3	BCR-PDGFRA.B1P13
PDGFRA	BCR- PDGFRA.B7in s24P12	Fusion	3	BCR-PDGFRA.B7ins24P12
PDGFRA	CDK5RAP2- PDGFRA.C13i ns40P12	Fusion	3	CDK5RAP2-PDGFRA.C13ins40P12
PDGFRA	DIP2C- PDGFRA.D1P 10	Fusion	3	DIP2C-PDGFRA.D1P10
PDGFRA	DIP2C- PDGFRA.D1P 11	Fusion	3	DIP2C-PDGFRA.D1P11
PDGFRA	ETV6- PDGFRA.E6P1 2	Fusion	3	ETV6-PDGFRA.E6P12
PDGFRA	FIP1L1- PDGFRA.F10P 12del47	Fusion	3	FIP1L1-PDGFRA.F10P12del47
PDGFRA	FIP1L1- PDGFRA.F10i nt10P12del106	Fusion	3	FIP1L1-PDGFRA.F10int10P12del106
PDGFRA	FIP1L1- PDGFRA.F10i nt10P12del22	Fusion	3	FIP1L1-PDGFRA.F10int10P12del22
PDGFRA	FIP1L1- PDGFRA.F10i nt10P12del67	Fusion	3	FIP1L1-PDGFRA.F10int10P12del67

	,			,
Gene Name	Variant ID	Variant Type	Level of Evidence Code	аМОІ
	FIP1L1-			
PDGFRA	PDGFRA.F11P 12del24	Fusion	3	FIP1L1-PDGFRA.F11P12del24
FDGFRA	FIP1L1-	Fusion	3	FIFTET-FDGFRA.FTTFT2uei24
	PDGFRA.F11P			

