PDGRB	ETV6- PDGFRB.E7in s34P12	Fusion	3	ETV6-PDGFRB.E7ins34P12
PDGRB	GIT2- PDGFRB.G12 P11	Fusion	3	GIT2-PDGFRB.G12P11
PDGRB	GOLGA4- PDGFRB.G10 P11	Fusion	3	GOLGA4-PDGFRB.G10P11
PDGRB	GOLGB1- PDGFRB.G10 P12	Fusion	3	GOLGB1-PDGFRB.G10P12
PDGRB	HIP1- PDGFRB.H30 P11	Fusion	3	HIP1-PDGFRB.H30P11
PDGRB	KANK1- PDGFRB.K2P9	Fusion	3	KANK1-PDGFRB.K2P9
PDGRB	MPRIP- PDGFRB.M20 P12	Fusion	3	MPRIP-PDGFRB.M20P12
PDGRB	MYO18A- PDGFRB.M41 P10	Fusion	3	MYO18A-PDGFRB.M41P10
PDGRB	NDE1- PDGFRB.N6P 11	Fusion	3	NDE1-PDGFRB.N6P11
PDGRB	NIN- PDGFRB.N30 P12	Fusion	3	NIN-PDGFRB.N30P12
PDGRB	PDE4DIP- PDGFRB.P16P 11	Fusion	3	PDE4DIP-PDGFRB.P16P11
PDGRB	PRKG2- PDGFRB.P3P1 2	Fusion	3	PRKG2-PDGFRB.P3P12
PDGRB	PRKG2- PDGFRB.P6P1 2	Fusion	3	PRKG2-PDGFRB.P6P12

				g
Gene Name	Variant ID	Variant Type	Level of Evidence Code	аМОІ
PDGRB	RABEP1- PDGFRB.R14 P11	Fusion	3	RABEP1-PDGFRB.R14P11
PDGRB	SART3- PDGFRB.S15P 11	Fusion	3	SART3-PDGFRB.S15P11
PDGRB	SPECC1- PDGFRB.S3P1 1	Fusion	3	SPECC1-PDGFRB.S3P11
PDGRB	TNIP1- PDGFRB.T14P 11	Fusion	3	TNIP1-PDGFRB.T14P11
PDGRB	TP53BP1- PDGFRB.T23P 11	Fusion	3	TP53BP1-PDGFRB.T23P11
PDGRB	TPM3- PDGFRB.T7P1 1	Fusion	3	TPM3-PDGFRB.T7P11
PDGRB	TRIP11- PDGFRB.T16P 11	Fusion	3	TRIP11-PDGFRB.T16P11
PDGRB	WDR48- PDGFRB.W9P 12	Fusion	3	WDR48-PDGFRB.W9P12
PDGRB	ZEB2- PDGFRB.Z9P9	Fusion	3	ZEB2-PDGFRB.Z9P9

List of Exclusion Variants:

Gene Name	Variant ID	Variant Type	Level of Evidence Code	аМОІ
KIT	COSM1311	SNV	2	p.D816H
KIT	COSM1310	SNV	2	p.D816Y
KIT	COSM24675	SNV	2	p.D816A
KIT	COSM12711	SNV	3	p.D816G
KIT	COSM1314	SNV	2	p.D816V
KIT	COSM19285	SNV	3	p.D816E
KIT	COSM12710	SNV	2	p.D820Y
KIT	COSM133670	SNV	2	p.D820A
KIT	COSM1316	SNV	2	p.D820G
KIT	COSM12709	SNV	2	p.D820E
KIT	COSM19280	SNV	2	p.D820E
KIT	COSM1318	SNV	2	p.N822H
KIT	COSM1321	SNV	2	p.N822K
KIT	COSM1322	SNV	2	p.N822K
KIT	COSM18681	SNV	2	p.Y823D
KIT	COSM13172	SNV	2	p.A829P

Molecular Analysis for Therapy Choice (MATCH) MATCH Treatment Subprotocol V: Sunitinib

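### Appendix II lists KIT COSM18681 p.Y823D as both an inclusion and an exclusion variant, and nothing in the protocol says which list governs

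*Protocol*

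**What the plan says.** Three parts of the protocol bear on this variant.

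- **Criterion 2.1.2.** The molecular criterion opens with "Patients must have a somatic cKIT mutation in exon 9, 11, 13 or 14, excluding exon 17 or 18 mutations". After naming activating PDGFRA and PDGFRB changes, it goes on to "or another aberration, as identified via the MATCH Master Protocol and described in Appendix II". It then refers the reader to Appendix II for both the inclusion and the exclusion mutations and their levels of evidence.
- **Appendix II.** Under the heading "List of Inclusion Variants", one KIT row reads "COSM18681 SNV 3 p.Y823D". In the exclusion list that follows, a KIT row reads "COSM18681 SNV 2 p.Y823D". The introduction to the appendix describes an automated rule in MATCHBOX, which may take in "known activating missense mutations in exons 9, 11, 13, and 14 of the KIT gene at Level of Evidence code 2".
- **Section 1.2, efficacy according to genotype.** The stated intent is "We will exclude patients with exon 17 and 18 cKIT mutations from this trial".

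Section 2 allows no waivers and says that registering someone who does not meet every criterion "can result in the participant being censored from the analysis of the" study.

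**The concern.** The variant identifier, variant type and amino-acid change are identical in the two rows; only the status and the level of evidence differ. A site or a matching algorithm that reads the inclusion table would assign the patient, and one that reads the exclusion table would not. Both tables are current operative text, and both rows are complete, so this is neither superseded wording nor damage from reading the PDF.

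Two things are at stake. The first is who gets treated. Section 1.2 describes exon 17 mutants in GIST as strongly resistant to sunitinib, and reports a median PFS of 2.3 months with secondary exon 17 or 18 mutations against 7.8 months with exon 13 or 14. If Y823D belongs to the first group, the inclusion row lets in patients whom the stated rationale meant to keep out.

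The second is the primary endpoint. Whether a treated carrier failed 2.1.2, and so could be dropped from the analysis, depends on which row is applied. If that is decided after the response is known, the denominator is no longer fixed in advance.

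**Working it through.** The protocol gives no figure to reproduce here. The check is a comparison of the lists, followed by a bound on the effect.

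**1. Overlap between the lists.** The exclusion list has 16 KIT rows: codon 816 (6 rows), 820 (5), 822 (3), 823 (1) and 829 (1); 6 + 5 + 3 + 1 + 1 = 16. Matching variant identifiers against the inclusion list gives one hit, COSM18681.

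| | Inclusion list | Exclusion list |
|---|---|---|
| Variant ID | COSM18681 | COSM18681 |
| Type | SNV | SNV |
| Change | p.Y823D | p.Y823D |
| Level of evidence | 3 | 2 |

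**2. Position.** The three highest KIT codons on the inclusion list are 823 (Y823D), 802 (H802T) and 697 (H697Y). Y823D is therefore the only KIT inclusion row within the range the exclusion list spans, 816 to 829. The document has no codon-to-exon map, so placing Y823 in exon 17 or 18 is an inference from that range.

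**3. Is there a tie-break?**
- Criterion 2.1.2 excludes exon 17 and 18 mutations but leaves a route in through Appendix II, and it points to both lists without ranking them.
- The MATCHBOX rule concerns exons 9, 11, 13 and 14 at level 2. The inclusion row for Y823D is at level 3, so that rule does not explain it.
- Section 1.2 states an intent by exon, not by variant.

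None of these is a precedence rule.

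**4. Size.** Assume that all 35 patients of the accrual goal (Schema) enter the response rate, with r responders.
- Changing one patient's outcome moves the rate by 1/35 = 2.9 points.
- Censoring one non-responder moves it by r/34 − r/35 = r/1190. Censoring one responder moves it by r/35 − (r − 1)/34 = (35 − r)/1190. Neither exceeds 34/1190 = 2.9 points, so 2.9 points is the ceiling per patient.
- For typical values, take 20-29%, the response range Section 1.2 gives for imatinib in KIT-mutant melanoma, purely as an assumption. With one non-responding carrier, 7/35 = 20.0% against 7/34 = 20.6% (0.6 points), and 10/35 = 28.6% against 10/34 = 29.4% (0.8 points).
- If a non-responding carrier instead takes the place of a patient who would respond at that rate, the expected loss is 0.20/35 = 0.6 to 0.29/35 = 0.8 points.

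**The case against.** The best reply is that the intent is plain and the row is a clerical slip. An exclusion list normally overrides an inclusion list. Section 2 requires every criterion to be met, 2.1.2 rules out exons 17 and 18, and Section 1.2 says the same. Reading the phrase about other aberrations so as to readmit a KIT mutation that the same sentence excludes is strained. Assignment is also made through the Master Protocol and MATCHBOX, which may already settle precedence, and Section 2 names officers for eligibility questions. Finally, a shift of 0.6 to 0.8 points is about a tenth of a standard error: at 7/35 the standard error is √(0.2 × 0.8/35) = 6.8 points.

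Much of this stands. Exclusion is the likelier intent, no misassignment has been shown, and the numerical effect is small. But the argument from intent needs Y823 to lie in exon 17 or 18, which the document never says. If exclusion prevails, the inclusion row is wrong; if the inclusion row was deliberate, the exclusion row is wrong. A rule in the Master Protocol would decide which row governs but would leave two rows that disagree on status and level of evidence.

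Other repeats suggest that the tables were not reconciled: COSM1253 p.V559G is on the inclusion list at level 2 and again at level 3, and COSM1246 p.K558N appears there twice. Those do not alter eligibility. The Y823D pair does.

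**Conclusion.** The concern holds. For this one variant the eligibility text contradicts itself, and this document offers no rule to resolve it. That conclusion rests only on the two rows and on the absence of a precedence statement; it needs no view on which row is correct.

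The effect is likely small: at most 2.9 points of response rate per affected patient, and about 0.6 to 0.8 points in the assumed 20-29% range. Those figures assume 35 analysed patients and at least one enrolled carrier. The frequency of the variant is not given, so the number of carriers could be zero. The exon placement of Y823 is inferred, and the other KIT inclusion rows, H802T among them, cannot be checked against the exon rule without an exon map. The point should still be fixed, because it sits in the operative eligibility table under a no-waiver rule with a possible consequence for the analysis set.

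**What to change.** - Reconcile 2.1.2, Section 1.2 and the two lists in Appendix II so that COSM18681 has one status and one level of evidence. Deleting the inclusion row would agree with the exclusion list and, if the sponsor confirms that Y823 lies in exon 17 or 18, with 2.1.2 and Section 1.2 as well.
- Add one sentence saying which list governs when a variant appears on both, or cite the Master Protocol section that says so.
- Confirm that the list held in the matching software agrees with the corrected appendix, and clear the repeated V559G and K558N rows at the same time.
- Before the primary analysis, identify any patient assigned on this variant and record, without reference to response, whether that patient is counted.

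The cost is one table row, one sentence, and a check of the software list and of assignments to date. No extra patients or procedures are needed.

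### Appendix II lists KIT p.Y823D as both an inclusion and an exclusion variant, and its exclusion list does not say whether it carries the whole exon 17/18 exclusion of Section 1.2 and criterion 2.1.2

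*Protocol*

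**What the plan says.** The exon 17/18 exclusion appears in three places in the Protocol.

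- Section 1.2, under efficacy by genotype, states it by exon and without qualification: "We will exclude patients with exon 17 and 18 cKIT mutations from this trial".
- Criterion 2.1.2 repeats it by exon: "Patients must have a somatic cKIT mutation in exon 9, 11, 13 or 14, excluding exon 17 or 18 mutations". The same criterion also admits activating PDGFRA or PDGFRB variants and fusions, "or another aberration, as identified via the MATCH Master Protocol and described in Appendix II". It refers to that appendix for "information on the inclusion and exclusion mutations".
- Appendix II has an inclusion list and, at its end, a table headed "List of Exclusion Variants".

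The inclusion side opens with a rule that works by exon: "A function has been implemented in MATCHBOX to identify any in-frame insertions and deletions in exon 9, 11, 13, and 14 of the KIT gene". The next sentence widens it: "This function may include any in-frame insertions, deletions or known activating missense mutations in exons 9, 11, 13, and 14 of the KIT gene". The paragraph closes with "Please refer to Section 1.4.2 of the MATCH Master Protocol for more information". No comparable text stands beside the exclusion table.

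Section 2 of the Protocol allows no waivers. All of its criteria must be met, and registering a patient who fails one can lead to that patient being censored from the analysis and to a major violation at audit.

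**The concern.** Appendix II is where the exon rule becomes named variants, so site, assignment system and analyst should all reach the same answer from it. There are two obstacles.

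First, p.Y823D is on both lists. A patient whose tumour carries it meets an inclusion entry and an exclusion entry at once, and the document gives no order of precedence.

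Second, the exclusion is worded by exon in two places, but the table that 2.1.2 points to names individual variants only. A reader cannot tell whether the table illustrates the exon rule or limits it.

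What is at stake is the eligible population for the primary objective, the response rate in patients with c-KIT mutations. The exclusion has a stated reason: Section 1.2 reports, in GIST treated with sunitinib, a median progression-free survival of 2.3 months with secondary exon 17 or 18 mutations against 7.8 months with secondary exon 13 or 14 mutations. A patient assigned on one reading and judged ineligible on another could be dropped from the response-rate denominator.

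**Working it through.** The plan states no figure to reproduce here. The check is a count of the exclusion table and a comparison of the two lists.

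**Step 1. Count the exclusion rows (Appendix II, last table).**

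| Codon | Rows | Distinct protein changes |
|---|---|---|
| 816 | 6 (D816H, Y, A, G, V, E) | 6 |
| 820 | 5 (D820Y, A, G, and E twice) | 4 |
| 822 | 3 (N822H, and K twice) | 2 |
| 823 | 1 (Y823D) | 1 |
| 829 | 1 (A829P) | 1 |
| Total | 6 + 5 + 3 + 1 + 1 = 16 | 6 + 4 + 2 + 1 + 1 = 14 |

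All 16 rows are typed as SNV. None is an insertion or deletion, and no line states an exon-level rule.

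**Step 2. Compare with the KIT rows of the inclusion list.** Only SNV rows can match, because every exclusion row is an SNV. Exactly one variant is common to both:

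- inclusion list: KIT, COSM18681, SNV, Level of Evidence 3, p.Y823D;
- exclusion list: KIT, COSM18681, SNV, Level of Evidence 2, p.Y823D.

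Gene, identifier and protein change agree; only the Level of Evidence differs. These are two entries for one variant with opposite effect.

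**Step 3. Follow p.Y823D through 2.1.2.** By the inclusion list it can qualify as an aberration described in Appendix II. By the exclusion list it disqualifies. The exon wording also points to disqualification if codon 823 lies in exon 17 or 18. The Protocol gives no codon boundaries, so that location is an inference from the variant's place on the exclusion list. The contradiction between the lists does not depend on it.

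**Step 4. Follow an unlisted exon 17/18 mutation.**

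- Alone: the tumour would normally have no qualifying variant, so the patient is not assigned on either reading.
- Beside a qualifying variant: the words of Section 1.2 and 2.1.2 bar the patient; the 16 rows taken alone do not.

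The scopes therefore give different answers only in the second case, and only if assignment applies the rows without the exon wording.

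**Step 5. Size.** The Protocol gives no rate for such co-occurrence outside GIST and no frequency for p.Y823D, so an expected number cannot be derived. Per affected patient, against the accrual goal in the Schema, the share is 1/35 = 2.9%.

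**The case against.** The strongest reply is that a general rule followed by a list of named variants is not a contradiction. Nothing in 2.1.2 says that Appendix II narrows the exon rule or is exhaustive. Section 1.2 agrees with 2.1.2, and Section 2 requires every criterion to be met, so an unlisted exon 17/18 mutation is already barred. This stands. A reader might infer that the short list lets such patients in; the documents do not support that. They do not say how the exclusion is run in practice, and the Master Protocol, which is not among the documents, may hold the matching rule. Section 2 also names offices to which eligibility questions can be put.

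A reader might also take the codons with no exclusion row, or inclusion rows at high codon numbers, as evidence of omitted or misplaced variants. That inference fails too. The rows are individually catalogued variants rather than a tiling of codons, and no exon boundaries are given. Criterion 2.1.2 also admits other aberrations described in Appendix II.

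The reply does not reach p.Y823D. One could say that an exclusion normally overrides an inclusion, but the Protocol states no such precedence. If it applied, the inclusion row would have no effect and should not be there.

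**Conclusion.** The point holds as a minor one, in two parts of unequal weight.

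The firm part is p.Y823D: the appendix cannot be followed as written for this variant, because it both qualifies and disqualifies the same patient. This rests on the text alone.

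The weaker part is scope. The exclusion table is narrower than the exon wording it serves and does not say what it is, whereas inclusion has an exon-level function. This is a missing statement rather than a conflict of rules. It has a practical effect only under two assumptions that the documents do not settle: that assignment runs on the lists, and that an unlisted exon 17/18 mutation occurs beside a qualifying variant.

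The documents do not show that any patient was or will be wrongly assigned; the number may be zero. Each affected patient would be 2.9% of the accrual goal. Section 2 says that ineligible registration can lead to censoring, not that it must. No sample-size or error-rate figure depends on the point.

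**What to change.** Reconcile Section 1.2, criterion 2.1.2 and Appendix II in one edit. Which molecular scope is intended is for the sponsor to decide.

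1. Keep p.Y823D (COSM18681) on one list only.
2. Add one sentence beside the exclusion list. It should say either that the exclusion covers all KIT exon 17/18 mutations and the 16 rows are named examples, or that it covers only the listed variants. If the Master Protocol already sets the rule, cite that section there instead.
3. Word Section 1.2 and 2.1.2 to match the choice.

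The cost is one deleted row and about one sentence, possibly with a change to the matching rule if the exon-wide scope is chosen and not yet implemented. Each choice has a consequence to accept knowingly. Under the exon-wide scope, an occasional patient is not assigned. Under the listed-variants scope, a tumour with an unlisted exon 17/18 mutation beside a qualifying variant is eligible.
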